## 6.0 Study Intervention/Investigational Agent

**6.1 Description:** Tirosint®-SOL (levothyroxine sodium) is a ready-to-use clear, colorless to slightly yellow oral solution containing LT4. It is supplied in 1 mL white single-dose ampules. Inactive ingredients are glycerol and water. IBSA Pharma Inc. will provide Tirosint®-SOL for the study at the following strengths (mcg/mL): 13, 25, 38, 50. Commercially available LT4 tablets will also be used in the study. Inactive ingredients vary between formulations. LT4 tablets for the study will be supplied in the following strengths (mcg): 25, 50, 75. Children's Mercy IDS Pharmacy will store, handle, and dispense the study drug per Research Pharmacy SOP for the Control of Investigational Drugs.

## 6.2 Drugs or Biologics:

Drug/Biologic Name	FDA Approval Status and Use in this Study
Tirosint®-SOL	FDA approved, and being used within FDA labeling
Levothyroxine sodium	FDA approved, and being used within FDA labeling

## PARTICIPANT MANAGEMENT

### 7.0 Inclusion and Exclusion Criteria

#### 7.1 Eligibility Criteria:

##### Inclusion Criteria

- Participant is at least 2 months old and less than 10 years of age
- Prior confirmed diagnosis of Trisomy 21
- Prior confirmed diagnosis of congenital or acquired hypothyroidism
- Currently takes levothyroxine sodium by mouth
- Gestational age >35 week

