### 2.0 Objectives

**2.1 Purpose, specific aims, or objectives:** Hypothyroidism is a common medical disorder in children with Trisomy 21 (T21). Treatment with oral tablet levothyroxine (LT4) is primarily used to treat this condition. However, children with T21 have developmental delay and other functional gastrointestinal (GI) issues that may negatively affect LT4 tolerability and absorption. For an age group unable to swallow tablets whole by mouth, tablets must be crushed and suspended in water, breast milk or formula for administration to treat children with hypothyroidism. For this age group, ease of administration may have a significant impact on compliance and ability to remain euthyroid. Until recently, there was no liquid preparation of LT4 in the United States for use in children.

Tirosint®-SOL (liquid stable LT4) is now FDA-approved for use in children. We propose that Tirosint®-SOL will be more favorably received due to ease of administration, improved tolerability, and palatability, therefore leading to improved adherence when compared to LT4 tablets. Our aims for this study are as follows:

- **Aim 1:** *Utilize medication tolerability questionnaire, CareCAT, to understand parental perceptions of liquid stable LT4*
- **Aim 2:** *Evaluate differences in ease of use of liquid stable LT4 compared to LT4 tablets*
- **Aim 3:** *Compare biochemical effect of liquid stable LT4 versus tablet LT4 on TSH and FT4 in T21 hypothyroid patients*

**2.2 Hypothesis:** We hypothesize that Tirosint®-SOL will be biochemically comparable to tablet LT4 as well as tolerated well and accepted by children with T21 and hypothyroidism ages 2 months to < 10 years. Caregivers will perceive Tirosint®-SOL as a preferred dosage form.

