## 4.0 Study Endpoints

- 4.1 Primary endpoint:** *Parent perception responses from CareCAT medication tolerability tool*
- 4.2 Secondary endpoint:** *TSH and FT4 drawn 8-weeks post intervention*
- 4.3 Tertiary endpoint:** *linear growth (height), weight gain, and head circumference growth*

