## 5.0 Study Design

**5.1 Study Design:** This is a single-center, pilot, randomized, open-label, cross-over study to determine satisfaction of standard LT4 tablets compared to liquid stable LT4 (Tirosint® -SOL) therapy and biochemical comparability in 22 participants diagnosed with Trisomy 21 and congenital or acquired hypothyroidism already on levothyroxine (LT4). Participants will be randomized in a 1:1 ratio to treatment (Tirosint®-SOL) or control (conventional therapy with LT4 tablets) for 8 weeks, at which point they will then crossover to receive the treatment arm they were not initially randomized to receive.

Participants will continue their same daily dose of LT4 or Tirosint®-SOL within the randomly assigned treatment group. Dose adjustments are allowed as needed, based on laboratory results and clinical response. Once enrolled, participants will be treated for 16 weeks total. The study will involve up to 3 in-person visits and 2 safety phone calls. Enrollment visit may be done via approved CMH video conferencing platform.

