### **13.0 Risks to Participants**

**13.1** The risk for Levothyroxine and Tirosint®-SOL are the same and may include shortness of breath, irregular heart rate, heart attack, muscle spasms, headache, nervousness, irritability, insomnia, tremors, muscle weakness, increased appetite, weight loss, diarrhea, heat intolerance, and skin rash. It is possible to have an allergic reaction to the other additional components included in either study drug. Allergic reactions usually happen right away after taking the medicine by mouth and symptoms include having a rash. These reactions are very rare. Participants will be on levothyroxine regardless of study participation, so there is no increased risk with study participation

**13.2** The researchers believe the risks involved in this study are not greater than minimal risk

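### Does an entry criterion that names no formulation let children already on the test liquid into the trial, and does that spoil the comparison?

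*Protocol*

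**What the plan says.** Among the inclusion criteria in Protocol section 7.1, the only one on current treatment is "Currently takes levothyroxine sodium by mouth". The single exclusion about how medicine is given concerns G-tube or parenteral administration. No exclusion mentions current or past use of a liquid.

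The protocol uses the drug's name in two ways:

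- **As a generic name covering both forms.** Section 6.1 describes Tirosint-SOL as follows: "levothyroxine sodium) is a ready-to-use clear, colorless to slightly yellow oral solution containing LT4". Section 5.1 describes the children as having "congenital or acquired hypothyroidism already on levothyroxine (LT4"), and in the same sentence calls the test product liquid stable LT4.
- **As the name of the comparator.** Section 6.2 lists "Levothyroxine sodium" in a row of its own, apart from Tirosint-SOL. Section 5.1 says "Participants will continue their same daily dose of LT4 or Tirosint®-SOL", and section 13.1 says "The risk for Levothyroxine and Tirosint®-SOL are the same". In all three places the name stands opposite the liquid.

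Section 4.1 gives the primary endpoint as "Parent perception responses from CareCAT medication tolerability tool". On how common prior liquid use might be, section 2.1 says that tablets are the main treatment, that the liquid is now approved for children, and that "Until recently, there was no liquid preparation of LT4 in the United States for use in children".

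**The concern.** An eligibility criterion is applied as written. This one is met by a child whose current treatment is the test product, because that product is oral levothyroxine sodium. Such a child is conceivable: the liquid is approved for children, and section 9.1 allows outside referrals and self-referral as well as recruitment from the clinic's own list.

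The endpoint makes this worth a look. The study is open-label, the outcome is a caregiver's opinion, and section 2.2 expects caregivers to prefer the liquid. A caregiver who already gives the liquid rates a familiar product against an unfamiliar tablet, the reverse of what a tablet family does. Randomising the order of treatments does not balance this, because the entry formulation stays with the child through both periods. If prior use raises the liquid rating, it raises that child's liquid-minus-tablet difference whichever treatment comes first. That child's baseline TSH and FT4 would also be values on the liquid. At stake would be a primary comparison tilted, plausibly towards the liquid, by children who had already been using it.

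**Working it through.** **Reading the text.** The criterion must be read against the rest of the protocol.

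1. Section 7.1 uses the exact name that section 6.2, immediately before it, gives to one of two products. The other product there is Tirosint-SOL. On that vocabulary the criterion means the comparator, that is, tablets.
2. Sections 5.1 and 13.1 make the same two-way contrast. Section 5.1 also calls tablets the conventional therapy.
3. Against this stand the generic name in section 6.1 and the phrase liquid stable LT4 in section 5.1. They show that the name can cover both forms. They do not say that liquid users were meant to enter.
4. No section says the target population is tablet-treated. The synopsis defines it as children with Trisomy 21 and hypothyroidism. A liquid user who entered would be inside the stated population.

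The wording is therefore loose, the likely reading is tablets, and the other reading contradicts nothing.

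**Size if a liquid user did enter.** The protocol has no figure to reproduce: the copy at hand gives no count of liquid users, no CareCAT standard deviation and no sample-size calculation. What follows is an illustration.

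- From the protocol: 22 children, randomised 1:1 (sections 5.1 and 8.1), so 11 per sequence if the split is even.
- Assumed: c children on the liquid at entry, c = 0, 1, 2 or 4; and a constant shift d in each one's liquid-minus-tablet difference, d = 0.5, 1 or 2 SD of the within-child differences.

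Shift in the mean difference = c × d / 22, in SD:

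| Children on liquid at entry | d = 0.5 | d = 1 | d = 2 |
|---|---|---|---|
| 0 | 0 | 0 | 0 |
| 1 | 0.023 | 0.045 | 0.091 |
| 2 | 0.045 | 0.091 | 0.182 |
| 4 | 0.091 | 0.182 | 0.364 |

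Does randomised order cancel the shift? Put k of the c children in one sequence and c − k in the other. The crossover estimate averages the two sequence means, so it moves by

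(k × d/11 + (c − k) × d/11) / 2 = c × d / 22,

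whatever k is. The order does not cancel it. This follows from assuming a constant shift; it is no evidence that a shift exists.

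For scale, the 95% half-width for a paired mean with 22 children is t(0.975, 21)/√22 = 2.080/4.690 = 0.443 SD. One child with a 1 SD shift is 0.045/0.443, about 10% of that. The most extreme cell is 0.364/0.443, about 82%, and it needs four liquid users with very large shifts. Section 2.1 gives no support for that many: tablets are the main treatment and the liquid is recent.

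**The case for a change.** The strongest case for a change is that eligibility belongs in the protocol and cannot be left to an analysis plan, that the ambiguity is real on the page, and that naming the formulation would cost a few words. The protocol also uses levothyroxine generically elsewhere: the synopsis speaks of levothyroxine therapy where both arms are meant, and section 21.1 speaks of a child who no longer needs it. So section 6.2 does not settle the meaning beyond argument. And a bias is not excused merely because it is smaller than a confidence half-width.

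Much of this stands. The criterion is ambiguous, and one consistent name would be tidier. What is missing is a consequence. The number of liquid users is unknown and may be zero, the size of any shift is assumed, and its direction is uncertain.

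Nor would the obvious remedy remove the problem. With tablets-only entry, every family compares a familiar tablet with a new liquid. Prior experience becomes the same for all 22 families, but it is still there, and nothing in the protocol shows that uniform familiarity with the comparator distorts less than a mixture. The restriction could also lose eligible children from a 22-child pilot.

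What else might be asked for is largely provided or belongs elsewhere. The table of events in section 5.2 already schedules a medical history and a concomitant medication review at Visit 1, where the current product would naturally be noted. Reporting CareCAT with and without any liquid user is a sensitivity analysis, a matter for a statistical analysis plan that is not shown.

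**Conclusion.** No change follows. The gap in section 7.1 is one of terminology: the same name serves as the generic term in section 6.1 and as the comparator's name in section 6.2. Staff would most likely read the criterion as tablets, and if one or two liquid users entered, the trial would still make a sound within-child comparison in a population the protocol describes.

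On the assumed inputs the mean moves by nothing with no such child, by 0.02 to 0.09 SD with one, and by up to 0.36 SD with four children each shifted by 2 SD, against a half-width of 0.44 SD. These figures show scale only; the document supports no claim of actual bias.

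The conclusion rests on prior liquid use being rare, as section 2.1 suggests, and on no tablets-only target being stated elsewhere. Several later sections, including procedures, surveys and statistical analysis, appear only as headings in the copy at hand, so that second point cannot be checked throughout. Several children entering on the liquid would be a reason for a sensitivity analysis, not for a different design.

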##### Exclusion Criteria

- Gestational age ≤35 weeks
- Participant currently takes anticonvulsant medication
- Participant takes medication through G-tube or another parenteral route
- Participant has more than 2 missed SOC clinic visits in the last 2 years
- Participant has documented history of noncompliance with levothyroxine
- Participant is currently in foster care or state custody

#### 7.2 Vulnerable Populations: Check any vulnerable populations that are being targeted for enrollment into the study: (Members of the following populations may not be included as participants in the research unless selected here.)

 Children/Minors (under 7 years of age)	 CM Employees
 Children/Minors (7-17 years of age)	 CM Students/Residents/ Fellows
 Neonates (infants less than 30 days old)	 Economically or Educationally Disadvantaged Persons
 Neonates of Uncertain Viability (infants less than 30 days old)	 Prisoners
 Non-Viable Neonates (infants less than 30 days old)	
 Wards of the State	
 Fetuses	
 Pregnant Women	
 Adults with impaired decision-making capacity	

- We will enroll children between the ages of 2 months and < 10 years, therefore meeting the definition of children as a vulnerable population. Participants may also have developmental delays. Study rationale, procedures, risks, and benefits will be explained prior to enrollment by one of the study team members using plain English with minimal medical terminology. The research staff will ensure that the potential participant's parent(s)/LAR understand that participation is voluntary. Parent/LAR will be assured that their child's research records will be kept confidential and will only be available to study personnel. To minimize coercion, parent(s)/LAR will be reassured that participation in no way influences or impacts their child's medical treatment. This research does not include other vulnerable populations including neonates, pregnant women, prisoners, or cognitively impaired adults. It is possible that a CMH employee's child may be eligible for this study. In this event, they will be allowed to participate. The employee will be reassured that participation is voluntary. If the research involves enrolling CM employees or students, indicate how the potential for employees/students to feel coerced or unduly influenced to participate will be minimized. For example, the risk of coercion may be minimized by ensuring that employees will not be recruited or enrolled by their direct supervisor.

## **8.0 Local Number of Participants**

**8.1** A total of 22 subjects will be enrolled in this study. Study participation will last approximately 4 months.

## **9.0 Identification and Recruitment of Potential Participants**

**9.1 Identification of Potential Participants:** Patients may be identified from the CMH Endocrine Clinic outpatient visit schedule, by a list of potential eligible patients through a batch medical chart review from IT, individual chart review, or through outside referrals. Research staff may approach parent(s)/LAR of eligible patients during Endocrine Clinic visits, by phone, or by email. Patients may also be referred by Downs Syndrome Clinic providers. Baseline visit may occur in Downs Syndrome Clinic with approval of Down Syndrome Clinic Medical Director. Potential participants may also self-refer in response to posted advertisements. Study team members may contact potential participants no more than three times to determine interest in this study. Contact attempts and refusals will be documented in the pre-screening log. Refusals will not be approached further.

**9.2 Pre-Screening prior to HIPAA Authorization:** In accordance with 45 CFR 164.512(i)(1)(ii), qualified participants will be identified and recorded initially by creation of a pre-screening log. The pre-screening log will be maintained to aid in participant identification and eligibility status. This will aid key study personnel in efficiently and effectively attending clinic visits for optimal recruitment. PHI may be collected and stored in pre-screening log and may contain, names (participant and

parents/LAR), address, phone number, email address, medical record number, date of birth, age, clinic visit date, clinic location, clinic provider & appointment time, diagnoses, as well as coordinator/investigator notes regarding eligibility/scheduling. A Waiver of HIPAA is being requested for recruitment purposes only. Data from subjects who are determined ineligible or chose not to participate will be kept until the completion of enrollment to avoid approaching them multiple times. When enrollment is complete, this data will be deleted for patients that did not enroll.

**9.3 Recruitment of Potential Participants:** IRB-approved recruitment flyers may be distributed at the CMH Endocrine and Down Syndrome Clinics and the Down Syndrome Guild of Greater Kansas City. The study may also be advertised using the recruitment flyer in the employee announcement bulletin board (Scope), internal employer website, or email.

## **10.0 Procedures**

### **11.0 Surveys:**

### **12.0 Sharing of Results with Participants**

**12.1** Results of study labs will be provided to parents of subjects. No other study data will be shared with subjects

### **13.0 Risks to Participants**

**13.1** The risk for Levothyroxine and Tirosint®-SOL are the same and may include shortness of breath, irregular heart rate, heart attack, muscle spasms, headache, nervousness, irritability, insomnia, tremors, muscle weakness, increased appetite, weight loss, diarrhea, heat intolerance, and skin rash. It is possible to have an allergic reaction to the other additional components included in either study drug. Allergic reactions usually happen right away after taking the medicine by mouth and symptoms include having a rash. These reactions are very rare. Participants will be on levothyroxine regardless of study participation, so there is no increased risk with study participation

**13.2** The researchers believe the risks involved in this study are not greater than minimal risk

## **14.0 Potential Benefits**

**14.1** Patients may benefit from improved tolerability of administration of the study drug. Subject may have improved biochemical response and absorption to medication, evaluated by TSH & LT4 lab results.

## **16.0 Payment, Reimbursement and Tangible Property provided to participants**

## **17.0 Economic Burden to Participants**

## **18.0 Permission/Accent/Consent Process**

**18.1** Indicate below all methods of Permission/Consent that will be used in this study:

**18.2 Assessment of Ability to Assent:** Study staff will ask parent(s)/LAR if their child has been diagnosed with any developmental or cognitive delay. If yes, study staff will ask if parent(s)/LAR feel the participant is at or above the cognitive and development level of an average 7-year-old. Any child 7 years and older and at a cognitive or developmental level typical of an average 7-year-old will be assented. Study staff reserve the right to withhold assent on any participant deemed ineligible due to cognitive or development level based solely on the assessment of the study staff. Assessment of ability to assent will be documented in consent note per CMH research policy.

**18.3 Permission/Accent/Consent Discussion:** Consent and assent discussion may take place in one of the CMH Endocrine Clinic locations, by phone, or approved CMH video conferencing platform per CMH research policy. Consent discussions conducted in person will be held in a private room. Consent and assent will be presented by designated study staff to parent(s)/LAR. Parent(s)/LAR and participants will be reminded that research is voluntary and will be provided ample time to read, review, and ask questions about participating in the research study. Parent(s)/LAR and participant will be provided and allowed the opportunity to meet with the PI privately to discuss consent if requested. Parent(s)/LAR and participant will be provided a copy of the consent to take home to allow for more time if needed. Person giving consent and assent will utilize teach back to confirm understanding prior to

signing of consent and assent. Parental consent and participant assent will be verbally confirmed prior to performing study procedures at every visit.

## **19.0 HIPAA and Confidentiality**

**19.1** Full Written HIPAA Authorization will be obtained withing the permission/consent from. A Partial Waiver of HIPAA Authorization for Recruitment Only will be requested as described in section 9.2.

**19.2** Research staff will emphasize that participate in research is voluntary and that participants may withdraw at any time without penalty. Verbal permission to continue participation in study will be obtained at the beginning of every study visit. All procedures will be explained with an opportunity for parent(s)/LAR to ask questions prior to proceeding with study procedures

## **20.0 Provisions to Protect the Privacy Interests of Participants**

### **21.0 Withdrawal of Participants**

**21.1** Participants may be withdrawn by study staff at any time for an issue with study compliance, any concerns of harm to the participant, or if study labs reveal that the participant no longer needs levothyroxine (at the discretion of the PI). Participants may also be withdrawn if the study staff or CMH Research Compliance discover any issues that could compromise the safety of the participants or the integrity of the study data. Any participant withdrawals will be discussed with the PI and documented by the study coordinator in a research note in the electronic medical record.

**21.2** All data collected prior to participant withdrawal will be retained by the study. Participants will be asked to return all study medication, both unused and empty packaging to the study coordinator to be returned to IDS Pharmacy for drug accountability. Participants will be instructed to continue their regular care with their Endocrine provider

## **22.0 Data Collection**

## **23.0 Adverse Events and Unanticipated Problems**

**23.1 Monitoring:** Parent(s)/LAR of participants will be asked at every study visit if there have been any changes to the participant's health status since the last contact. Any change in medical history after enrollment visit will be considered an AE and will be documented. Any open AE/SAE at the end of study will only be followed if the PI has determined it is related to study participation.

Open AE/SAEs attributed to study participation will be followed until resolved or the discretion of the PI.

## **24.0 Statistical Analysis**

## **25.0 Data and Specimen Management**

## **26.0 Setting & Location**

**26.1** This study will be conducted at any of the CMH Endocrine Clinics or virtually through a CMH approved video conferencing platform. No community advisory boards will be involved in the research study. No study procedures will be conducted outside of the CMH organization. Participants will be given contact information for both the PI and lead Nurse Coordinator. If laboratory results reflect a need in dose change, the child's provider will be consulted for that decision. No other anticipated medical or psychological resources are anticipated.
